5. STUDY DURATION

Following enrollment, each patient will be maintained in the study for 12 months.

Estimated date of first subject enrolled: May 2019

Estimated date last subject to complete the study (12 month follow-up): May 2021

6. NUMBER OF PATIENTS

A total of 240 patients will be enrolled for the study. The enrollment will occur over a 12 month period.

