4. PATIENT POPULATION

General Consideration:

The study population is composed of de novo solitary kidney transplant recipients who meet inclusion and exclusion criteria and have not been subject to investigational treatments.

Enrollment Rationale: The Multicenter Transplant Alliance Kidney Consortium collectively transplants more than 1,500 people each year (10% of the total number of kidney transplants in the United States annually). Approximately 60% of these patients will be eligible for this study. We consider a 12 month enrollment time to be a conservative estimate.

Clinical Study Protocol [#SIMPLE]

Screening Failure: Subjects who do not meet the eligibility criteria as outlined below during the screening phase of the study will be considered screening failures.

Inclusion criteria:

Each patient must meet all of the following inclusion criteria to be enrolled in the study:

- Patient is an adult (18 years of age or older).
- Treatment with Envarsus XR® or immediate-release, twice-daily tacrolimus has been indicated by patient's transplant care team.
- Patient is a recipient of a deceased or living donor kidney transplant.
- Patient is able to comply with study procedures for the entire length of the study.
- Patient has been informed about the study survey and has signed an informed consent form.

Exclusion criteria:

Patients meeting any of the following exclusion criteria are not to be enrolled in the study:

- Patient is unable or unwilling to complete study patient reported outcome questionnaires.
- Patient is currently receiving azathioprine
- Patient is currently receiving an mTOR inhibitor (sirolimus, everolimus)
- Patient is currently receiving an belatacept
- Patient has received investigational immunosuppression 1 month prior to transplant or post-transplant
- Patient is in a setting where a professional care taker is responsible for dispensing subject's medication.

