8. TREATMENT ASSIGNMENT

This is an observational study, and as such, treatment will not be assigned, and there is no intervention. The treatment decision will be made by each patient's transplant care team, independent of the study.

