17. STATISTICAL ANALYSES

Interpretation of scores and score differences in patient-reported measures can be a difficult task since the scales lack the clinical meaning that is inherent in measures of survival, serum concentrations, or anthropometric values. To aid in interpretation of these scores, differences are often standardized by dividing by the standard deviation in the sample to calculate an effect size. There are general guidelines for small, moderate, and large effects on this standardized scale that can be applied to any outcome measure. A standardized effect size (mean difference / standard deviation) less than 0.20 is considered clinically insignificant in the field of patient-reported outcomes research, while effect sizes of 0.30 - 0.40 are generally considered to be minimally important to moderate in magnitude.

For the CIRS, which had a standard deviation of 3.6 in a sample of patients receiving cyclosporine, an effect size of 0.30 corresponds to a difference of 1 point on the 0-20 scale. In the control group, we expect a mean CIRS score similar to or higher than that seen in a sample of patients receiving cyclosporine (3.8 +/- 3.6). A 1 point reduction in the Envarsus XR® group would be equivalent to a 30% reduction in calcineurin inhibitor-related symptoms.

A total of 240 patients will be enrolled. Estimating 15% study dropout provides 204 patients with complete data at the study endpoint, which will allow us to detect effect sizes of 0.28 or larger for the difference between treatment arms with a 2-sided 0.05 level of significance and 80% power in for individual patient reported outcome measure items. This sample size is also appropriately powered to compare adherence rates between groups. Based on assumptions of 75% and 90% mean adherence, respectively, in the 2 groups (and standard deviations of 38% and 30%, respectively), a sample size of 110 per group will yield 90% power to obtain a significant difference between the 2 groups, using a 2-sample t test at a 2-sided 0.05 level of significance.

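### Section 17 states power for groups of 110, but enrolment sets only a total of 240 and leaves formulation to the care teams, so the claim needs restating for 204 completers at a stated split

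*Combined protocol and SAP*

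**What the plan says.** Section 6 gives the enrolment rule: "A total of 240 patients will be enrolled for the study. The enrollment will occur over a 12 month period". Section 7 repeats the total and describes a two-group comparison without an allocation ratio. Section 8 says "This is an observational study, and as such, treatment will not be assigned, and there is no intervention", and adds: "The treatment decision will be made by each patient's transplant care team, independent of the study". Under Section 4 a patient on either drug qualifies: "Treatment with Envarsus XR® or immediate-release, twice-daily tacrolimus has been indicated by patient's transplant care team".

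Section 17 then makes two power statements.

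- **Patient-reported outcomes.** "Estimating 15% study dropout provides 204 patients with complete data at the study endpoint", which is said to be enough to "detect effect sizes of 0.28 or larger for the difference between treatment arms" at two-sided 0.05 and 80% power. No group sizes are given.
- **Adherence.** With means of 75% and 90% and SDs of 38% and 30%, "a sample size of 110 per group will yield 90% power to obtain a significant difference between the 2 groups". This is the only statement that gives group sizes.

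No section states the expected share on each formulation, a minimum or maximum per formulation, or a rule for watching the mix as it accrues.

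**The concern.** For a fixed total, the precision of a two-group difference depends on how the total is divided. Patients added to the larger group contribute little once the smaller group limits the comparison. Randomisation, or a quota on invitations, would hold the groups near equal. This design has neither, so recruitment ends at 240 whatever the mix.

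The stated power therefore describes a study that the enrolment rule does not deliver. A reader of the results would take 80% and 90% as the sensitivity of the comparisons, when the real figures depend on prescribing habits that the plan neither predicts nor records as a design assumption. The adherence statement also uses 220 patients, whereas the same paragraph expects 204 with complete data.

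**Working it through.** **Inputs, all from Section 17.** 240 enrolled; 15% dropout; adherence means 75% (immediate release, IR) and 90% (Envarsus XR); SDs 38% and 30%; two-sided 0.05. I assume the same dropout in both groups and take the 204 completers as the patients with usable adherence data.

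**Step 1: the plan's own figures.**

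- Completers: 240 × 0.85 = 204.
- Adherence at 110/110: standard error = √(38²/110 + 30²/110) = 4.616, and 15/4.616 = 3.249. Power is Φ(3.249 − 1.960) = 90.1% by the normal approximation and 89.9% by the unequal-variance (Welch) t test. The stated 90% reproduces.
- Two groups of 110 need 220 completers. At 15% dropout that means 220/0.85 ≈ 259 enrolled, even with a perfect 1:1 split.

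**Step 2: adherence power with 204 completers.** Standard error = √(38²/n_IR + 30²/n_XR), difference 15, Welch t test with Satterthwaite degrees of freedom. The splits are assumptions.

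| Split (completers) | IR smaller | Envarsus XR smaller |
|---|---|---|
| 50:50 (102/102) | 87.6% | 87.6% |
| 40:60 (82/122) | 84.6% | 87.8% |
| 30:70 (61/143) | 77.4% | 84.8% |
| 20:80 (41/163) | 63.6% | 76.1% |

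The normal approximation is higher by 0.3 to 1.6 points (for example 78.2% and 65.2% with IR smaller at 30:70 and 20:80). The columns differ because IR has the larger SD, so a small IR group costs more.

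**Step 3: detectable effect on the CIRS.** If the smaller group has share p of a fixed total, the detectable effect is multiplied by 1/(2√(p(1−p))), relative to equal groups:

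- 40:60: 1/(2 × 0.490) = 1.02
- 30:70: 1/(2 × 0.458) = 1.09
- 20:80: 1/(2 × 0.400) = 1.25

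These multipliers do not depend on the SD or on adjustment for baseline.

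**Step 4: what they multiply.** Unadjusted, 102/102 detects (1.960 + 0.842) × √(2/102) = 0.392 SD at 80% power, not 0.28. Reaching 0.28 through baseline adjustment needs √(1 − ρ²) = 0.28/0.392 = 0.714, so ρ ≈ 0.70, a correlation the plan does not state.

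| Split | Unadjusted | If ρ = 0.70 |
|---|---|---|
| 50:50 | 0.392 | 0.280 |
| 40:60 | 0.400 | 0.286 |
| 30:70 | 0.428 | 0.306 |
| 20:80 | 0.489 | 0.350 |

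Section 3 hypothesises an effect of 0.29 SD. Even if ρ = 0.70 holds, that effect stays detectable at 80% power at 40:60 (0.286) but not at 30:70 (0.306).

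**The case against.** The strongest reply is that the harm depends on an unknown. The documents give no formulation share, and nothing in them makes a lopsided split likely or unlikely. At 40:60 the CIRS detectable effect rises by only 2%, and adherence power moves by at most 3 points from its 50:50 value. This stands, and it is why the result is a range. A reader might infer that the groups will be badly unbalanced, for instance 192 against 48 enrolled at 20:80. The documents do not support that as a prediction.

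A reader might also infer that imbalance would pull primary-endpoint power from 80% down to 61% at 20:80. That series starts from 80% at 102/102, which holds only with the unstated correlation of about 0.70. Unadjusted, power for 0.28 SD is already 51.6% with equal groups. Only the multipliers can be relied on, and the unexplained 0.28 is a separate problem.

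A third tempting step is to require 120 per formulation and close each as it fills. This would respect the care team's choice, since the study decides only whom to invite. But it would leave late enrolment on one drug, confounding treatment with calendar time, and with site if prescribing differs between centres. The Section 17 ANCOVA adjusts only for baseline score and would not remove this. It would also leave 102 completers per group, not 110. The documents do not support closure as a plain improvement.

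Finally, this is called a pilot, and Section 17 reports an adjusted difference and an effect size. Calling a null result uninformative would therefore go too far. The plan still makes explicit power claims, and those should match the design.

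**Conclusion.** The point holds as a mismatch between the stated power and the enrolment rule. Two parts are certain from the documents: nothing in Sections 6 to 8 produces equal groups, and 204 completers cannot give 110 in each under any split. The size of the further loss is conditional. Against the stated 90%, adherence power on 204 completers falls short by about 2 points at 50:50, 2 to 5 at 40:60, 5 to 13 at 30:70 and 14 to 26 at 20:80. Imbalance becomes material for the CIRS from roughly 30:70.

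These figures rest on the plan's own means and SDs, equal dropout in both groups, and adherence data from all 204 completers. If adherence were analysed on everyone enrolled, two groups of 110 would fit within 240, but only near 1:1, and Section 17 does not say that this is intended.

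**What to change.** In Section 17, drop the 110-per-group statement. Restate adherence power and the CIRS detectable effect for 204 completers at the expected formulation split, or at the observed split if enrolment has closed, with a range of splits beside it. State the baseline correlation behind any adjusted figure. This is a text change. Its cost is a less favourable stated figure.

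The second case looks the more likely: this version is dated 8 April 2021, and Section 5 estimates the last 12-month visit in May 2021, which would put the end of enrolment around May 2020.

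If enrolment is still open, add a running count by formulation in REDCap and consider a soft minimum for the smaller group. Section 4 puts the yearly pool at more than 1,500 transplants and says "Approximately 60% of these patients will be eligible for this study", so about 900. A formulation with a 10% share would offer about 90 patients a year, so a minimum of 96 (40% of 240) could not be met in 12 months even with full consent. Any closure of one formulation should be optional, and the amendment should state the risk of confounding with calendar time and site.

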7. STUDY DESIGN

Study Center(s): Multicenter Transplant Alliance – Kidney Centers

Study Design: This is a prospective, multi-center, observational, open-label, study comparing transplant-specific patient reported outcomes and medication adherence between Envarsus XR® and immediate release tacrolimus medication in adult renal transplant recipients. The study will enroll 240 patients and survey these same 240 patients at three time points during the study.

Clinical Study Protocol [#SIMPLE]

Study Design Rationale:

Patients will be enrolled into the study within the first 30 days post-transplant. Treatment will not be determined by this study, and there is no intervention. The treatment decision will be made by each patient's transplant care team, independent of the study.

For the primary objective, comparison of calcineurin inhibitor related symptoms, a standard two-group design will be used to compare treatment groups. These groups will also be compared for transplant-related symptoms, health-related quality of life, adverse events, patient satisfaction, adherence, dnDSA, and graft function.

8. TREATMENT ASSIGNMENT

This is an observational study, and as such, treatment will not be assigned, and there is no intervention. The treatment decision will be made by each patient's transplant care team, independent of the study.

9. STUDY METHODS AND PROCEDURES

General: Transplant recipients will be cared for according to the site's standard of care (SOC) protocols employed for post-transplant follow-up. The investigator at the site will be directly responsible for supervising the care of these recipients during the length of the study.

Products Studied:

- Tacrolimus (twice daily immediate release (IR) oral formulation) or
- Envarsus XR® (a once daily extended-release oral tacrolimus formulation).

Envarsus XR® is an FDA approved medication and is indicated for the prevention of organ rejection in de novo kidney transplant patients in combination with other immunosuppressants

Medication Safety and Efficacy: Renal function, occurrence of biopsy proven acute rejection, development of dnDSA, and occurrence of adverse events will be assessed throughout the duration of the study as collected as part of standard of care or as part of study. Please see Criteria for Evaluation (Section 17) for detailed description of monitoring techniques.

Patient-Reported Measures:

- Patients will complete surveys on their own unless they are unable to. Surveys will be administered on tablets so that data will be recorded in the study's database immediately and securely. The following patient reported outcome measures will be assessed at both study visits.
 - HRQoL: PROMIS -29 profile (29 questions) measuring depression, anxiety, fatigue, pain interference, sleep disturbance, physical function, participation in social roles, and pain intensity
 - Symptoms: Calcineurin-inhibitor related symptoms (5 items) and the Transplant related symptoms (15 items) – items from PRO-CTCAE or in PRO-CTCAE format.
 - Symptoms/Tolerability: FACT- G (GP5) – Single item bothersome assessment (1 question).
 - The PROMIS Self-Efficacy for Managing Medication and Treatment (26 questions).

Clinical Study Protocol [#SIMPLE]

- The Transplant Satisfaction Questionnaire for Medication – question 14.

10. DEVIATION FROM TREATMENT REGIMEN

If deviation occurs from treatment, patient will continue study. Patient reported outcome measures will be completed as scheduled and samples will be taken as scheduled. Reason(s) for deviation will be recorded.

Criteria for Study Termination

The investigator can discontinue the study participant at any time for any reason, including development of severe adverse events, uncontrolled infection, or other clinical/administrative reasons. Allograft loss and death will be cause for automatic withdrawal from the study. If a patient unable to continue the study for any reason, an early termination visit is necessary to complete the study. If the patient needs to be started on immunosuppression that is listed in the exclusion criteria of this study, an early termination visit is necessary to complete the study.

11. STUDY DRUG STORAGE, DISPENSING, AND ACCOUNTABILITY

Patient will receive open label drug through their pharmacy of choice.

12. CONCOMITANT MEDICATIONS

Subjects are required to take immunosuppressive medication to maintain allograft function. The patients will be on the following immunosuppression medications in addition to tacrolimus at the time of study entry per the inclusion criteria:

- *Mycophenolate Mofetil (CellCept®) or Mycophenolate Sodium, Enteric Coated (Myfortic®) (MMF) or generic equivalent formulations.* Target MMF doses will be between 1000 – 3000 mg/day in divided doses or the enteric coated equivalent delivered by mouth twice daily. The MMF dosage will be decreased or discontinued in the presence of adverse events as clinically warranted. Dose reduction or discontinuation will be documented. Adverse events that may warrant dosage modifications of MMF include but are not limited to gastrointestinal (gastritis, diarrhea, nausea, vomiting, dyspepsia) or hematological (leukopenia, thrombocytopenia, anemia or neutropenia). MMF may be resumed at the full dose or at a reduced dose after resolution of symptoms or the patient may receive an alternate adjunctive immunosuppression per the investigator's discretion as long as they are not those listed in the exclusion criteria.
- *Corticosteroids.* Low dose once daily oral prednisone (5-10 mg) may be administered per each site's standard of practice. Doses may be increased at the discretion of the investigator. This most commonly occurs after pulse steroid treatment for rejection.
- *Belatacept, mTOR inhibitors, azathioprine, and investigational immunosuppression* will not be allowed in this study. Patient who are deemed to require one of these medications should be removed from the study and undergo an early termination visit to complete the study.

13. TREATMENT COMPLIANCE

All subjects in the study will be adequately informed on the specific tacrolimus formulations the patients will receive throughout the study and the importance of compliance to the study protocol.

Clinical Study Protocol [#SIMPLE]

14. TIMING OF VISITS

Visit 1: Baseline/Screening

To be collected within the first 30 days post-transplant

- Informed consent
- Demographics
- Medical history
- Complete physical exam including vital signs, height, and weight
- Determination of eligibility based on inclusion/exclusion criteria
- Hematology panel
- Electrolytes including creatinine and eGFR
- Urinalysis
- Baseline Surveys:
 - HRQoL: PROMIS -29 profile (29 questions) measuring depression, anxiety, fatigue, pain interference, sleep disturbance, physical function, participation in social roles, and pain intensity
 - PRO-CTCAE: Calcineurin-inhibitor related symptoms (5 items) and the Transplant related symptoms (14 items)
 - FACT – G (GP5): Single item bothersome assessment (1 question)
 - The PROMIS Self-Efficacy for Managing Medication and Treatment (26 questions) – (study visit 1 only).

Visit 2: Day 120 ± 30 days

All subjects will complete the following prior to morning tacrolimus administration:

- Vital signs, height, and weight
- Hematology panel
- Electrolytes including creatinine and eGFR Tacrolimus trough
- Surveys including:
 - HRQoL: PROMIS -29 profile (29 questions) measuring depression, anxiety, fatigue, pain interference, sleep disturbance, physical function, participation in social roles, and pain intensity
 - PRO-CTCAE: Calcineurin-inhibitor related symptoms (5 items) and the Transplant related symptoms (14 items)
 - FACT – G (GP5): Single item bothersome assessment (1 question)

Visit 3: Day 365 ± 45 days (end of study visit)

All subjects will complete the following prior to morning tacrolimus administration:

- Vital signs, height, and weight
- Hematology panel
- Electrolytes including creatinine and eGFR Tacrolimus trough
- Surveys including:

Clinical Study Protocol [#SIMPLE]

- HRQoL: PROMIS -29 profile (29 questions) measuring depression, anxiety, fatigue, pain interference, sleep disturbance, physical function, participation in social roles, and pain intensity
- PRO-CTCAE: Calcineurin-inhibitor related symptoms (5 items) and the Transplant related symptoms (14 items)
- FACT – G (GP5): Single item bothersome assessment (1 question)
- The Transplant Satisfaction Questionnaire for Medication – question 14.

SCHEDULE OF EVENTS

	Baseline (Within the first 30 days post- transplant)	4 Months Post- Transplant	12 Months Post- Transplant (End of Study)
STUDY VISIT NUMBER	1	2	3
Test/Procedures/Data Collection			
Informed Consent	X		
Review of Inclusion/Exclusion Criteria	X		
Demographics	X		
Medical History	X		
Adverse Event Assessment		X	X
Physical exam including vital signs and weight	X	X	X
Safety labs ¹	X	X	X
Tacolimus trough levels		X	X
Data collection from medical records pertaining to infection, immunosuppression, and graft function	X	X	X
Patient Reported Outcome Assessments			
PROMIS – Self-Efficacy for Managing Medications and Treatments v1.0 (26 items)	X		
PROMIS-29 Profile 2.1 (29 items)	X	X	X
Calcineurin Inhibitor Related Symptoms (CIRS) - (5 PRO-CTCAE items)	X	X	X
Transplant Specific(14 PRO-CTCAE items)	X	X	X
Patient Satisfaction: Treatment Satisfaction Questionnaire for Medication-Question 14 (1 question)			X
FACT-G (GP5)	X	X	X

1 Safety Labs (CBC with differential, Electrolytes including creatinine and eGFR)

15. DATA COLLECTION

Data will be collected at each of the MTAK sites and entered into REDCap. REDCap is a secure web application for building and managing online surveys and databases. REDcap is secure and will be managed by Mayo Clinic Rochester. REDcap is 21 CFR Part 11, FISMA, and HIPPA compliant and hosted on Mayo Clinic's secure servers.

Demographic information: Sex, race/ethnicity, transplant characteristics, and age will be collected.

Medical History: Data to be collected will include medical history and medications, pathologic and laboratory data that are in the pre and post-transplant record.

16. CRITERIA FOR EVALUATION

Safety

- AEs and SAEs will be assigned by Common Terminology Criteria for Adverse Events (CTCAE) terms and tabulated as incidence rates per tacrolimus formulation.
- Hematology parameters, blood chemistries, and urine results will be monitored regularly as part of the participating centers' standard of care.
- Vital signs, physical condition, and body weight measurements will be monitored regularly.
- Clinically significant infections (confirmed by culture, biopsy, genomic, or serologic findings) that requires hospitalization or active anti-microbial treatment will be tabulated as incidence rates per tacrolimus formulation.
- Cytomegalovirus (CMV), BK Virus, and Epstein-Barr disease will be tabulated as incidence rates per tacrolimus formulation.

Patient Reported Measures and Outcomes

- Patients will complete surveys on their own unless they are unable to. Surveys will be administered on tablets so that data will be recorded in the study's database immediately and securely. The following patient reported outcomes measures will be assessed:
 - HRQoL: PROMIS -29 profile (29 questions) measuring depression, anxiety, fatigue, pain interference, sleep disturbance, physical function, participation in social roles, and pain intensity
 - Symptoms: Calcineurin-inhibitor related symptoms (5 items) and the Transplant related symptoms (14 items) – items from PRO-CTCAE or in PRO-CTCAE format.
 - Symptoms/Tolerability: FACT- G (GP5) – Single item bothersome assessment (1 question).
- Adherence/Medication Satisfaction Measures: The following adherence tools/measures will be assessed at each study visit throughout the study for those patients capable of using an adherence measurement via a digital capture system:
 - The PROMIS Self-Efficacy for Managing Medication and Treatment (26 questions) – (study visit 1 only).
 - The Transplant Satisfaction Questionnaire for Medication – question 14.

